## 103 **1. Background and Summary**

### 104 **1.1 Epidemiology and Disease Burden**

105 Myopia (shortsightedness) is the most common eye condition in the world and is only increasing in  
106 prevalence, with studies predicting 4.7 billion afflicted by 2050. This increase in prevalence is  
107 particularly notable in East Asia, but myopia is increasing in the US as well: a study done with a  
108 contemporary American cohort in Southern California found that 41.9% of the cohort, aged 5-19 years  
109 old, were myopic. Although visual impairment caused by myopia is generally correctable (via glasses,  
110 contact lenses, etc.), uncorrected refractive error costs \$202 billion annually in global GDP. High  
111 myopia is associated with increased risks of glaucoma, cataracts, and retinal detachment.

### 112 **1.2 Current Treatments**

113 Slowing the progression of myopia has been attempted through a range of treatments with varying  
114 degrees of success. Among the most promising have been soft bifocal contact lenses, orthokeratology,  
115 and antimuscarinic agents (pirenzepine, atropine, etc.). However, these treatments are not without  
116 side effects: atropine can cause side effects such as photophobia, and orthokeratology carries the risk of  
117 microbial keratitis. In addition, compliance with contact lens wear can be poor.

### 118 **1.3 Myopia and Violet Light**

119 An abundance of studies have shown that outdoors exposure is protective against myopia onset.  
120 Meta-analysis indicates that one additional hour spent outdoors per week translated to a 2% reduced  
121 odds of developing myopia. Some studies have also shown that outdoor exposure can reduce myopic  
122 progression. The mechanism for this is yet unclear, but it has been theorized that violet light may be  
123 key to this protective effect. Due to overzealous UV protection, violet wavelengths have been rendered  
124 nearly absent from modern life despite being part of the visible spectrum: windows have very low  
125 transmittance for wavelengths below 400 nm, indoor lighting does not incorporate violet, and UV  
126 blocking glasses and contact lenses are abundant.

127 Previous studies by Torii et al. indicated that violet light is protective against myopia progression in  
128 humans. A retrospective study compared patients wearing non-violet transmitting eyeglasses, partially  
129 violet-blocking contact lenses, and violet light transmitting contact lenses, and found that patients  
130 wearing violet light transmitting contact lenses had a significantly decreased amount of myopia  
131 progression as measured by axial length elongation. Additionally, violet light was shown to influence  
132 high adult myopia: patients who received non violet light transmitting phakic intraocular lens  
133 implantations were significantly more myopic than patients who received violet light transmitting  
134 implantations.

135 Animal studies indicate that the light-sensitive protein OPN5 may be key in violet-light mediated  
136 suppression of myopia. OPN5 has previously been shown to regulate light-dependent vascular  
137 development in the murine eye via suppression of vitreal dopamine, which simultaneously increased  
138 retinal dopamine. This is significant because retinal dopamine has been widely hypothesized to  
139 antagonize myopia development. Violet light has been shown to reduce axial length elongation in  
140 chicks as well as stimulate a higher long-term retinal dopamine level than blue, red, or white light.

141 Most recently, OPN5 has been shown to be necessary for violet-light mediated suppression of lens  
142 defocus-induced myopia in mice. Violet light delivered for 3 hours in the evening (pre-dusk) protected  
143 mice from lens defocus-induced myopia, an effect that was shown to be both time and wavelength  
144 dependent – but did not protect OPN5 conditional null mice.

#### 145 **1.4 Role of Genetics in Myopia**

146 Large-scale genetic studies have been performed in myopia and have implicated the important role of  
147 genetic factors. Through molecular techniques, such as linkage analysis, association studies, and  
148 sequencing analysis, many of the genes associated with myopia have been identified. Furthermore, the  
149 prevalence of myopia increases significantly with the number of myopic parents; the associated  
150 development risk rates are 7.6% for no myopic parents, 14.9% for one myopic parent, and 43.6% for two  
151 myopic parents. The evidence is conclusive of a genetic contribution to myopia beyond environmental  
152 factors, and exploring the genetic component of patients with myopia is critical in better understanding  
153 the disease.

#### 154 **1.5 Bios SkyView Lamps**

155 In order to effectively deliver violet light, the BIOS SkyView lamp will be used. BIOS lighting uses  
156 patented circadian lighting technology to produce the highest melanopic to photopic lux ratio for a given  
157 color temperature, translating to better equivalent melanopic lux for a lower correlated color  
158 temperature than other LEDs. The BIOS SkyView lamps are equipped with wavelength-specific LEDs,  
159 able to provide a full profile of violet light (385 nm) for the purpose of this study. The SkyView lamps  
160 have been approved by CCHMC for research use (assessment ID: 109744). The Aooshine bedside lamps,  
161 which will act as the control light source, have also been approved by CCHMC for research use  
162 (assessment ID: 133975).

#### 163 **1.6 Impact of UV Blocking Lenses**

164 UV blocking glasses are ubiquitous in modern society. Pediatric patients are commonly prescribed  
165 polycarbonate eyeglasses due to their innate UV-blocking capabilities and shatter resistance. However,  
166 polycarbonate also attenuates the violet wavelengths that could potentially be crucial to myopia  
167 control. UV-blocking glasses, which typically seek to block wavelengths below 400 nm in an  
168 overabundance of caution, result in the elimination of much of the violet spectrum (380 nm to 450 nm),  
169 and could potentially be a contributing factor to the myopia epidemic.

#### 170 **4.9 Study Design**

##### 171 **A) Study Groups:**

172 To assess the effects of violet light and potential contribution from UV-blocking glasses, three study  
173 groups will be established:

- 174 1. A group (n = 24) will use the BIOS SkyView lamp with violet LEDs enabled for at least one hour  
175 during dawn and at least one hour during dusk. The group will wear CR-39 (UV-transmitting).
- 176 2. A group (n = 24) will use the BIOS SkyView lamp with violet LEDs enabled for at least one hour  
177 during dawn and at least one hour during dusk. The group will wear polycarbonate (UV-blocking)  
178 glasses for the duration of the study.

179 3. A group (n = 24) will use the Aooshine lamp without any violet LEDs enabled for at least one  
180 hour during dawn and at least one hour during dusk. The group will wear CR-39 (UV-  
181 transmitting).

182 The study lamp (BIOS or Aooshine) should be the sole source of artificial illumination in participant  
183 rooms for the duration of lamp exposure, and throughout the study, exposure to natural light during  
184 designated dawn and dusk times should be minimized. Light is a noninvasive source of therapy, and as  
185 such, tracking the actual exposure to the lamps and compliance to the study design can be difficult.  
186 Therefore, the HOBO Occupancy Sensor (UX90-005), which measures movements of heat emitted by  
187 people in motion via passive infrared technology, will be paired with each BIOS lamp.

#### 188 **B) Designating Dawn and Dusk**

189 The best times for the SkyView and Aooshine lamps to undergo the dawn and dusk transition will be  
190 chosen individually per participant based on their anticipated daily schedule to maximize effectiveness.  
191 Each participant will be given a survey prior to enrollment so that research staff can determine the  
192 optimal times on an individual basis.

193 The one-hour timeframe is chosen to be consistent with known biological responses and the length of  
194 the natural dawn/dusk transition. The SkyView/Aooshine lamp will automatically turn on at dawn and  
195 automatically turn off after dusk. Both dawn and dusk are chosen because while dusk exposure was  
196 protective in the murine myopia model, this effect may be present at dawn in diurnal mammals.

#### 197 **C) Onset HOBO Occupancy Sensor (UX90-005M)**

198 As light is a noninvasive form of treatment, assessing the amount of 'light' received is difficult to  
199 quantify in measuring the efficacy of violet light in slowing the progression of myopia. The Onset HOBO  
200 Occupancy Sensor uses infrared technology to measure fluctuations of temperature within a 5-meter  
201 radius. The temperature fluctuation readings are logged as numerical data which can then be  
202 retrospectively collected to then measure exposure to light during the duration of the study.

203

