## 218 **1.8 Study Objective**

219 The purpose of this short-term, pilot, randomized trial is to investigate the efficacy of violet light  
220 exposure through the BIOS SkyView Lamps at dawn and dusk versus non-violet light exposure through  
221 Aooshine Bedside Lamps in slowing the progression of myopia in school aged children as an alternative  
222 to current clinical treatments to determine whether to proceed to a full-scale longer-term randomized  
223 trial. This decision will be based primarily on assessing responses to light exposure by comparing  
224 treatment groups on the following outcomes:

- 225 • Axial length elongation
- 226 • Spherical refractive error
- 227 • Quality of life
- 228 • The proportion of participants reporting adverse effects
- 229 • The proportion of participants reporting >75% light exposure compliance

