### 408 **6.3 HOBO Sensor**

409 Participants will receive the HOBO sensor attached to their lamp. The sensor will be removable to bring  
410 to follow-up visits. Participants and guardians will be instructed how to remove the sensor properly, and  
411 how to put it back on the lamp.

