## 526 Secondary Analyses

- 527 • Difference in change in axial length at 6 and 12 months between the violet and non-violet light  
528 group
- 529 • Compliance will be assessed at each follow up and described as excellent (76%-100%), good  
530 (51%-75%), fair (26%-50%) or poor (<25%).

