## 531 **9.2 Decision Guideline**

532 The data collected in this short-term, pilot randomized clinical trial will primarily be used to determine  
533 whether to proceed to a full-scale, longer-term randomized trial of violet light vs control non-violet. The  
534 side effect profiles in the experimental and control groups will also be considered when deciding  
535 whether to proceed with a full-scale trial.

536 The decision guideline for determining whether to proceed to a full-scale randomized trial will be based  
537 on the primary and secondary outcomes at study conclusion.

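### The >75% compliance outcome that feeds the go/no-go decision is specified inconsistently: which lamps carry the sensor, what it measures, which source counts, and where the bands fall

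*Protocol*

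**What the plan says.** Protocol section 1.8 lists five outcomes on which the decision to proceed is primarily based, each compared between treatment groups. The fifth is "The proportion of participants reporting >75% light exposure compliance". Section 9.2 rests the decision "on the primary and secondary outcomes at study conclusion", and compliance appears under Secondary Analyses in 9.1.

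Three passages bear on how compliance is measured:

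- **Study Groups** (1.7 (A) in the table of contents, printed under a heading numbered 4.9) introduces an occupancy sensor "which measures movements of heat emitted by" "people in motion via passive infrared technology, will be paired with each BIOS lamp".
- **Section 1.7 (C)** says the "Occupancy Sensor uses infrared technology to measure fluctuations of temperature within a 5-meter" radius, and that its readings are "retrospectively collected to then measure exposure to light during the duration of the study".
- **Section 6.3** says: "Participants will receive the HOBO sensor attached to their lamp. The sensor will be removable to bring" to follow-up visits. It makes no distinction by lamp.

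Section 7.3 bases the compliance assessment at follow-up visits on the sensor data. Section 7.1 adds a daily emailed survey asking the parent when the lamp was used, as a second source to set against the sensor. Section 9.1 then grades compliance in four bands, the lower three being good ("51%-75%), fair (26%-50%) or poor (<25"%). The top band, excellent, is 76% to 100%.

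**The concern.** An outcome used for a go/no-go decision should have one meaning, measured in the same way in every arm. Here the protocol gives different answers on who carries the sensor, on what the sensor measures, and on whether the >75% figure comes from the sensor or from a report. Its bands also do not line up with its own cut-off.

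Two things are at stake. First, if the control lamps carried no sensor, the comparison in section 1.8 could not be made from sensor data, and data never recorded cannot be recovered later. Second, if occupancy is presented as light exposure, the decision would credit the trial with a measurement it does not make. Movement by a sibling or parent would count as the child's exposure, and a child sitting still might not count at all.

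**Working it through.** The protocol gives no expected compliance rate, so there is no stated figure to reproduce. The check sets the sections side by side and adds one illustration with assumed rates.

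**1. Which lamps carry the sensor.** Section 1.7 (A) names BIOS lamps only. That wording is narrower than the start of the same paragraph, which speaks of the study lamp as either BIOS or Aooshine. The schedule in section 3 has participants receive the sensor at Visit 2 and collects its data at 6 and 12 months, with no restriction by group. Sections 6.2 and 6.3 attach it to whichever lamp the child receives. Taken literally, 1.7 (A) gives sensor data for 24 + 24 = 48 children in the two violet groups and for 0 of 24 controls. That leaves 24/72 = 33% without data, all in one arm.

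**2. What is measured.** As described, the device registers moving body heat within 5 m. Nothing in the text has it record light, whether the lamp is on (an outlet timer controls that, section 6.4), or which person is in the room.

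Illustration, all rates assumed. Let *t* be the share of sessions the child attends, and *f* the share of missed sessions in which someone else triggers the sensor. The reading is *t* + (1 − *t*)*f*, which reaches 75% when *f* = (0.75 − *t*)/(1 − *t*):

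| True attendance *t* | *f* at which the reading is 75% |
|---|---|
| 50% | 0.25/0.50 = 50% |
| 60% | 0.15/0.40 = 37.5% |
| 65% | 0.10/0.35 = 28.6% |
| 70% | 0.05/0.30 = 16.7% |

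Error in the other direction: if a child attends 90% of sessions and motion is missed in 20% of those, the reading is 0.90 × 0.80 = 72%, below the cut-off. The protocol gives no information on how large *f* or the missed share would be.

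**3. Which source counts.** Section 1.8 counts participants who report compliance, which fits the survey. Section 7.3 records compliance from the sensor, and also mentions app data that is described nowhere else. Section 7.1 calls the survey a second source. No section says which of them yields the >75% figure.

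**4. The bands.** Values tested against 9.1 and 1.8:

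| Compliance | Band in 9.1 | >75% (1.8)? |
|---|---|---|
| 24.9% | poor | no |
| 25% | none | no |
| 25.5% | none | no |
| 50.5% | none | no |
| 75% | good | no |
| 75.5% | none | yes |
| 76% | excellent | yes |

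Rounding to whole percentages does not fully repair this. Exactly 25% stays unassigned, and 75.4% would round to 75 (good) although it exceeds 75%.

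**The case against.** The strongest case against is that this is mostly drafting. The schedule and sections 6.2, 6.3 and 7.3 all treat the sensor as universal, so controls will very probably have it. The protocol itself concedes that exposure to light is hard to track, and it provides a survey as a cross-check. The >75% cut-off and the excellent band are nearly the same. The denominator, and the rule for when sensor and survey disagree, could properly sit in an analysis plan that is not shown. Compliance is not the primary analysis, and 9.1 treats it descriptively.

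Much of this stands, and it rules out several stronger readings:

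- **That the outcome rests wholly on a motion sensor.** Section 7.1 supplies a second source. If reporting in 1.8 means the survey, the outcome may not use the sensor at all.
- **That controls will go unmeasured.** Only one sentence points that way, and the operational sections contradict it.
- **That the cut-offs conflict.** They differ only between 75% and 76%. The real conflict is over the data source.
- **That a null efficacy result could not be separated from non-use.** Sensor, survey, timer and telephone calls all bear on use, imperfectly.
- **That the sensor logs around the clock.** The text says only that readings are logged.
- **That misclassification is likely, or differs by arm.** The rates above are assumed.

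What the objection does not remove are the statements in this document that contradict each other or the device's own description. A later analysis plan cannot supply sensor data that were never collected.

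**Conclusion.** The point holds as an inconsistency in specifying a decision outcome. It does not show that compliance is unmeasurable or that the efficacy comparison fails. The firm parts need only the protocol's text:

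- 1.7 (A) contradicts sections 3, 6.2 and 6.3 on who gets the sensor.
- 1.7 (C) claims a measurement of light that the device, as described, does not make.
- 1.8 and 7.3 point to different sources for the same outcome.
- The bands leave exactly 25% unassigned and do not match >75% between 75% and 76%.

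The largest possible effect is loss of sensor data for all 24 controls, one third of the sample. It arises only if 1.7 (A) is followed literally, which is unlikely. The band defect is small. How often occupancy would put a child on the wrong side of 75% is unknown. The illustration shows only that, for a child close to the cut-off, triggering by others in about one in six missed sessions (16.7% at 70% true attendance) would be enough. This should be corrected, preferably before lamps are issued.

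**What to change.** 1. In 1.7 (A), pair the sensor with each study lamp (BIOS or Aooshine), matching sections 3, 6.2 and 6.3.
2. In 1.7 (C) and 7.3, call the sensor result room occupancy during the designated dawn and dusk sessions, not light exposure. Define it by session rather than by lamp-on time, because 1.7 (B) and 6.4 can be read as the lamp staying on from dawn to dusk.
3. In 1.8, name one source for the >75% outcome, the same in all arms. Report the other source alongside it, and show unanswered surveys separately rather than as non-use.
4. In 9.1, set the bands at ≤25%, >25–50%, >50–75% and >75%, so that excellent equals the decision outcome.

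A rule that counts a session only when both sources agree is tempting but should not be adopted. It would turn every unanswered email into non-use. With the assumed 72% reading above and an assumed, independent 80% survey completion, the score falls to 0.72 × 0.80 = 58%; completion of 60% to 100% gives 43% to 72%. It would still not confirm that the child was present, since the survey asks when the lamp was used.

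The cost is wording and a little more data processing, with no new device. The price is a more modest claim: compliance can be stated only as room occupancy or as reported lamp use.

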#### 204 **D) DNA Storage via Saliva**

205 In addition to exploring the efficacy of violet light exposure in treating myopia, the effects of genetic  
206 factors will be assessed from DNA extraction for research purposes only. In recent years, alongside the  
207 advent of more sophisticated molecular techniques such as linkage analysis, association studies, and  
208 sequencing analysis, many of the genes associated with myopia have been identified. Prevalence of  
209 myopia has proven to be significantly linked to genetics, and if conclusive findings are made from this  
210 study, further analysis of DNA collected from saliva could provide valuable information for posterity.  
211 Participants will be asked to spit 2-3 mL of saliva into a self-collection container provided by the study. A  
212 slight dryness in the mouth may occur; this will be a one-time collection. Collected saliva samples are for  
213 DNA extraction for the DNA to be banked for future, unspecified use. All future research accessing the  
214 samples or genetic datasets would be IRB approved and reviewed by the study team on a case-by-case  
215 basis.

216 Participants will be informed that they are donating genetic material, and the most likely outcome is that  
217 they will receive no further information regarding those samples.

## 218 **1.8 Study Objective**

219 The purpose of this short-term, pilot, randomized trial is to investigate the efficacy of violet light  
220 exposure through the BIOS SkyView Lamps at dawn and dusk versus non-violet light exposure through  
221 Aooshine Bedside Lamps in slowing the progression of myopia in school aged children as an alternative  
222 to current clinical treatments to determine whether to proceed to a full-scale longer-term randomized  
223 trial. This decision will be based primarily on assessing responses to light exposure by comparing  
224 treatment groups on the following outcomes:

- 225 • Axial length elongation
- 226 • Spherical refractive error
- 227 • Quality of life
- 228 • The proportion of participants reporting adverse effects
- 229 • The proportion of participants reporting >75% light exposure compliance

## 230 **1.9 Timing of Intervention and Outcome for Proposed Study**

231 To evaluate the response to violet light exposure for at least one hour at dawn and at least one hour at  
232 dusk compared to non-violet light exposure for at least one hour at dawn and at least one hour at dusk,  
233 this pilot randomized clinical trial (RCT) is proposed. If a reasonable initial response without significant  
234 adverse effects is found, a subsequent full-scale RCT would further evaluate the effectiveness of violet  
235 light exposure via the SkyView lamp for myopia treatment. We will define success as violet light  
236 exposure intervention demonstrating at least 80% non-inferiority compared to the control group.

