## 384 **5. Randomization**

### 385 **5.1 Randomization Process**

386 Participants eligible for randomization will be randomly assigned in a 1:1:1 distribution respectively to:

- 387 • Violet light experimental group (BIOS SkyView Lamp) with polycarbonate glasses
- 388 • Violet light experimental group (BIOS SkyView Lamp) with CR-39 glasses
- 389 • Non-violet control group (Aooshine Bedside Lamp) with CR-39 glasses

390 The investigator will construct a separate Master Randomization List using a permuted block design  
391 stratified by the treatment group. A participant is considered randomized when REDCap randomization  
392 process is completed.

393 The participant, parents, testers, and investigators will be masked to treatment group. If the need arises,  
394 the investigator may become unmasked after discussion of a specific case with the study team in  
395 response to any adverse events. The study coordinator will remain unmasked to the treatment group in  
396 order to facilitate the type of equipment and lenses the participant will need.

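### Section 1.9 defines success as non-inferiority to a non-violet control lamp, which a lamp with no effect can meet, while Section 1.8 asks whether violet light slows myopia

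*Protocol*

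**What the plan says.** Section 1.9 contains the protocol's only definition of success: violet light "exposure intervention demonstrating at least 80% non-inferiority compared to the control group". It attaches no outcome, scale, margin or confidence level. The preceding material in 1.9 makes a full-scale trial conditional on a response: "If a reasonable initial response without significant" adverse effects is found.

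Section 1.8 states the purpose as the efficacy of violet light versus non-violet light from "Aooshine Bedside Lamps in slowing the progression of myopia in school aged children as an alternative" to current treatments. It lists five outcomes: axial length, refractive error, quality of life, light-exposure compliance, and "The proportion of participants reporting adverse effects".

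The comparator appears only as a control. Section 1.5 says of the Aooshine lamps "which will act as the control light source, have also been approved by CCHMC for research use". Under Study Design, A) Study Groups, the third group "will use the Aooshine lamp without any violet LEDs enabled for at least one" hour at dawn and at dusk. Section 5.1 lists it as "Non-violet control group (Aooshine Bedside Lamp) with CR-39 glasses". Nowhere is it called an active myopia treatment.

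Section 9.1 compares 12-month change in cycloplegic spherical equivalent refraction (SER) and reports a violet versus non-violet difference with a 95% confidence interval. Section 9.2 bases the decision to proceed on the primary and secondary outcomes, with side effects also considered. Neither section mentions non-inferiority or 80%.

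**The concern.** Non-inferiority asks whether a treatment is not too much worse than its comparator. That is useful when the comparator is known to work. Here the comparator is a lamp without violet light, and the question is whether violet light adds a benefit. Being no worse than such a control does not show slowing, so the success definition points the wrong way for the stated objective. It also sits badly with the response that 1.9 itself asks for, because it can be met with no response at all.

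The pilot exists to decide whether a full-scale trial is worth running. At stake is a null result being reported as having met the protocol's predefined success.

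**Working it through.** **Can the criterion be reproduced?** No. The protocol gives no progression rate, SD, margin, alpha or power, and the 72 participants (24 per group) have no derivation. The 80% could be a retained fraction, a ratio, a confidence level, a power level or a share of participants.

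**The logic, without figures.** Let D be the extra myopic progression under violet light compared with control, in dioptres.
- Section 1.8 is answered in favour of violet light if D < 0.
- Non-inferiority with margin m > 0 is met if D < m.
- D = 0 (inert lamp) and any D between 0 and m (slightly adverse lamp) satisfy the second condition and fail the first.

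**Illustration on assumed inputs.** None of these is in the protocol, apart from the group sizes before loss:
- control progression P = 0.4, 0.6 or 0.8 D/year
- SD of 12-month change = 0.4, 0.5 or 0.6 D
- 80% read as a 20% allowance, so m = 0.2 × P
- 48 vs 24 (violet arms pooled) or 24 vs 24; with 20% loss, 38 vs 19 or 19 vs 19

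Formulas: SE = SD × √(1/n₁ + 1/n₂), which is 0.25 × SD for 48 vs 24 and 0.289 × SD for 24 vs 24. Point-estimate rule: pass probability Φ(m/SE) for an inert lamp. Confidence rules: noncentral t with noncentrality m/SE and critical t at 0.80 (one-sided 80%) or 0.975 (95% interval). For a lamp that worsens progression by 10%, m is replaced by m − 0.1 × P = 0.1 × P.

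Worked example: P = 0.4, SD = 0.6, 24 vs 24. Then m = 0.08, SE = 0.173, m/SE = 0.46 and Φ = 0.68. At the other extreme, P = 0.8, SD = 0.4, 48 vs 24 gives m = 0.16, SE = 0.10, m/SE = 1.6 and Φ = 0.945.

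| True effect | Retention | Point estimate | One-sided 80% | 95% interval |
|---|---|---|---|---|
| Inert | Full | 68%–95% | 35%–78% | 7%–35% |
| Inert | 20% loss | 66%–92% | 33%–72% | 6%–29% |
| 10% worse | Full | 59%–79% | 27%–48% | 4%–12% |
| 10% worse | 20% loss | 58%–76% | 26%–45% | 4%–10% |

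Within a column, the spread comes from the assumed progression, SD and split. The differences between columns reflect the ambiguity of the sentence.

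**The case against.** **Detail may sit in the analysis plan.** A missing margin, scale or endpoint could be supplied there and would not alone be a finding. That is fair. But the protocol itself chose to define success, and no margin chosen later makes non-inferiority to a non-violet control a test of slowing.

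**The term may mean safety or tolerability.** No-worse-than-control is coherent for adverse effects, quality of life or compliance, all listed in 1.8, and 1.9 does mention adverse effects. But 1.9 does not limit the term to those outcomes. Its surrounding language is about response and effectiveness, and nothing else in the protocol reconciles it with 1.8. Efficacy is the more natural reading.

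**The operative sections do not use the sentence.** This stands and limits the weight of the point. Section 9.1 gives the difference with its interval in any case, and 9.2 is not tied to 1.9. Neither excludes a non-inferiority reading, though: an interval can be set against a margin, and 9.2 has no threshold. So 1.9 remains the only predefined benchmark.

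**The figures rest on assumptions.** Also true. The only inferential level in the protocol is 95%, where an inert lamp passes 7% to 35% of the time at full retention, well below the point-estimate range. The conclusion does not depend on these figures.

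**A formal efficacy threshold is a lot to ask of a pilot.** The cost is real and is set out with the fix. A minimum-difference rule is less demanding than a significance rule.

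**Conclusion.** The concern holds. Read as an efficacy criterion, the definition in 1.9 contradicts the objective in 1.8, and Sections 9.1 and 9.2 neither use nor repair it. This follows from two things in the document: the control is presented only as a non-violet lamp, and the objective is to slow progression. How often an inert lamp would pass cannot be known from the protocol; the ranges above are illustrations.

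The consequence is confined to interpretation: a null or slightly adverse result could carry the label of success. It should be fixed, but it does not undermine the conduct of the trial or its estimates.

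**What to change.** In Section 1.9, drop non-inferiority for the efficacy outcome. Define success as less myopic progression than the non-violet control on the 9.1 estimate, in one of two ways:
- (a) a pre-specified minimum difference, read with its interval; or
- (b) an interval that excludes zero in favour of violet light at a stated level.

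Possible wording for (a): *Success is an estimated difference in mean 12-month SER change ([named violet arm or arms] minus non-violet control) of at least [X] D in favour of violet light, reported with its 95% CI.*

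The violet arm or arms must be named because a difference criterion in a three-arm trial cannot otherwise be applied. The choice matters: Section 1.6 says "polycarbonate also attenuates the violet wavelengths that could potentially be crucial to myopia" control, and one violet arm wears polycarbonate. Cite the same criterion in 9.2. Amend 9.1 only if a level other than 95% is chosen. A no-worse-than-control criterion can stay for adverse effects, quality of life or compliance if labelled as such.

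**Cost.** Wording only, with no added participants or procedures. The price is more false no-go decisions. The table uses an assumed mid case: progression 0.6 D, SD 0.5 D, and 30% slowing = 0.3 × 0.6 = 0.18 D. If the arms are pooled and the polycarbonate arm gains nothing, the average benefit is 0.18/2 = 0.09 D. X = 0.12 D is illustrative only. Interval rules use Φ(true/SE − z) with z = 1.96 or 1.28; the minimum-difference rule uses 1 − Φ((X − true)/SE). Figures in brackets are with 20% loss.

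| True difference | 95% CI rule | 80% CI rule | Estimate ≥ 0.12 D |
|---|---|---|---|
| 0.18 D | 24%–30% (20%–25%) | 49%–56% (43%–50%) | 66%–68% (64%–67%) |
| 0.09 D, pooled | 11% (9%) | 29% (26%) | 41% (42%) |
| 0 (inert) | 2.5% | 10% | 17%–20% (20%–23%) |

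The sponsor should choose the rule and X with this trade-off in view.
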